Thiamine as a Metabolic Resuscitator After Cardiac Arrest: Study protocol and statistical analysis plan

NCT03450707

Finalized and submitted to Clinicaltrials.gov: August 18 2022

Principal Investigator and corresponding author: [name]

[contact]

Introduction

The study protocol for Thiamine as a Metabolic Resuscitator After Cardiac Arrest is summarized in the original posting for the trial on [clinicaltrials.gov](https://clinicaltrials.gov/ct2/show/study/NCT03450707), NCT03450707. Additional details on the protocol and the statistical analysis plan are included in this document, which is being submitted for posting prior to initiation of any data analysis.

Methods

Trial Design

This is a randomized, double-blind, placebo controlled to investigate the effect of intravenous thiamine (vitamin B1) on lactate, cellular oxygen consumption, global oxygen consumption and biomarkers of neurologic injury in patients who achieve return of spontaneous circulation (ROSC) after an out-of-hospital cardiac arrest (OHCA).

Intervention:

Thiamine 500mg in 100mL 0.9% saline IV every 12 hours for 5 doses, with initial dose given within 4.5 hours of ROSC. Control arm will receive 0.9% saline of the same volume and frequency.

Consent/Exception from Informed Consent (EFIC):

This trial will be conducted under EFIC, as approved by the FDA and the Beth Israel Deaconess Medical Center Internal Review Board (IRB) following completion of community consultation and dissemination of information about the trial, including provision of the opportunity to opt out. EFIC will be utilized due to the need to enroll patients within 4.5 hours of ROSC. In line with the EFIC process, if the patient's legally authorized representative (LAR) is present, the research team will approach them for informed consent and the patient will be enrolled if the LAR consents. If the LAR is not present at the time of eligibility, the research team will make an attempt to contact them and provide them the opportunity to opt out of the trial. If the LAR is not reachable but a family member/next of kin is present or can be reached, that person will be provided the opportunity to opt out. If the LAR or family member does not opt out or if no LAR or next of kin can be reached, the patient will be enrolled in the trial. If a patient is enrolled under EFIC, the patient or the LAR will be approached for continuing consent as soon as this is possible.

Patient Population

Inclusion Criteria:

- Adult patient (age \geq 18 years)

- Cardiac arrest occurring with sustained (> 20 minutes) return of spontaneous circulation (ROSC)
- Lactate ≥ 3
- Within 4.5 hours of cardiac arrest event

Exclusion Criteria:

- Clinical indication for thiamine administration (alcoholism, known or highly suspected deficiency) or treatment with thiamine beyond the amount found in a standard multivitamin within the last 10 days
- Traumatic etiology of arrest
- Comfort measures only or anticipated withdrawal of support within 24 hours
- Protected populations (pregnant women, prisoners)
- Known allergy to thiamine

Randomization and blinding

Randomization: The randomization, completed by an independent statistician, will be generated using a random number generator via the use of the Statistical Analysis System (SAS) version 9.2 software, function RANUNI. Randomization will be 1:1, in blocks of 4. This function generates a random number between 0 and 1 from a uniform distribution function with parameter 0 and 1. If the random number is less than or equal to 0.5, the assignment is to the treatment group (coded A). If the random number is larger than 0.5, then the assignment is to the control group (coded B).

The research pharmacy, following the randomization list as above, will prepare and release study drug for each enrolled patient. Intravenous thiamine is odorless and colorless, and will be mixed in a 100mL bag of normal saline (NS). Patients assigned to the placebo arm will receive an identical volume of NS. Thiamine is odorless and colorless, and it is not possible to tell the difference between thiamine and placebo using this method. All study personnel with the exception of the research pharmacist will be blinded to the intervention. Unblinding will take place in the unlikely event of a case of suspected anaphylaxis or other severe reaction to study drug

Study Registration and Monitoring

The trial was registered at clinicaltrials.gov (NCT03450707) on March 1, 2018, prior to study start. Adverse events will be monitored by the PI and reported to the IRB and FDA as required. A Data Safety and Monitoring Board (DSMB) has been convened for this trial as required for any trial conducted under EFIC. DSMB meetings will occur at pre-planned

intervals of one year. There are no pre-specified stopping rules for futility or efficacy. No statistical interim analyses were planned.

Protocol:

Intervention: Thiamine 500mg IV in 100ml 0.9% saline every 12 hours for 48 hours (5 doses)

Placebo: 100ml 0.9% saline IV every 12 hours for 48 hours (5 doses)

Blood collection: Blood will be drawn at enrollment/time 0 (prior to study drug administration), 6 hours, 12 hours, 24 hours, 72, and 168 hours. Blood for all study labs will be collected by the patient's clinical nurse, using an existing intravenous or arterial line if present. Nursing or phlebotomy will perform a peripheral stick to obtain research blood only if no line is available for use. Research assistants will take all blood for immediate processing per the requirements of each lab test. Lactate and labs for SOFA score calculation will be processed in the BIDMC clinical lab. All other research assays (see list of secondary outcomes) will be completed in the BIDMC Center for Resuscitation Science Lab.

VO₂ monitoring: All patients meeting criteria for metabolic data collection (FiO₂ 60% or less and positive end expiratory pressure (PEEP) 15cm H₂O or less) will be connected to the VO₂ monitor at enrollment or as soon as the ventilator criteria are met, if still within 48 hours of enrollment. The monitor is made by General Electric, monitor version B650 with gas exchange module, and attaches in-line to the ventilator tube, between the endotracheal tube and the Y-connector. All connections and disconnections of the monitor will be done by a trained respiratory therapist, with study staff present at the bedside. The tubing is attached to sensors that collect data breath-by-breath and that data is continuously recorded while connected to a laptop with dedicated software for this purpose. At the end of the study protocol all data will be downloaded and stored in a secure CSV file.

Cerebral Performance Category (CPC) and Cerebral Performance Category-Extended (CPC-E) score assessments: CPC and CPC-E will be assessed just prior to hospital discharge, at 30 and 90 days. Research staff will approach patients for assessment of CPC-E prior to hospital discharge. The CPC-E includes several questions testing logical thinking, attention and memory. The outpatient portion, which will be assessed in addition to the inpatient portion after hospital discharge/at 30 and 90 days, also includes questions about functional status and return to work. The CPC score will also be assessed by research staff prior to discharge. Phone calls to the patient will be made at 30 and 90 days (if the patient is no longer in the hospital).

Outcome Measures

Primary Outcome: Lactate change

The primary outcome is change in lactate over 24 hours following enrollment.

Secondary Outcomes:

1. Absolute level and change in VO₂ over 48 hours
2. Absolute level of lactate over 72 hours
3. Absolute level and the change in pyruvate dehydrogenase (PDH) quantity, activity and specific activity over 72 hours
4. Absolute level and the change in S100 levels over 72 hours
5. Absolute level and the change in neuron-specific enolase (NSE) levels over 72 hours
6. Mortality (hospital discharge, 30 and 90 days)
7. Cerebral Performance Category (CPC) score (hospital discharge, 30 and 90 days)
8. Cerebral Performance Category-Extended (CPC-E) (hospital discharge, 30 and 90 days)
9. Absolute level and the change in Sequential Organ Failure Assessment (SOFA) Score SOFA over 72 hours
10. Acute renal failure during first 7 days following arrest
11. Absolute level and change in cellular oxygen consumption rate over 72 hours
12. Absolute level and the change in creatinine over 72 hours

Sample Size Calculations:

The analysis method for the primary endpoint will be linear mixed-effects modeling (LMM). This type of modeling is used in longitudinal or repeated-measures studies to take into account the correlation of within-subject measurements and can optimize the power. In this case, each subject will have lactate measurements at multiple time points, which are correlated. Since LMM will be used for the analysis, we have also used LMM for power analysis for this endpoint. We evaluated approximately 61 post-arrest patients in our databases for which we had lactate measurements over 24 hours and that matched the inclusion/exclusion criteria for the current proposal. We observed that the post-CA patients have a mean lactate of 3.8 ± 2.2 mmol/L at 6 hours, 3.5 ± 2.2 at 12-hours, and 2.9 ± 2 at 24-hours. We took a conservative position to assume that the potential effect size (the mean difference of lactate between the two groups) will be 33%. That is, we assumed that the mean lactate level at the three different time points were 2.55, 2.35, and 1.94. We then simulated the longitudinal data with the assumption that the variance-covariance structure of the lactate data followed a compound-symmetry structure with between-subject variance of 2.07. The linear-mixed effects model was used on the simulated data to obtain the estimated F statistic, numerator, and denominator degrees of freedom. From these estimates, the non-centrality parameter was computed and used to obtain the power. To obtain 80% power, with type-I error of 0.05, 66 subjects (33 thiamine, 33 placebo) will be needed to detect the stated difference over 6, 12, and 24-hours. We

secondarily performed calculations using the difference in means approach at the time point of 6 hours where we anticipate maximal effect of thiamine. At this time point, a reduction by 33% yields a power of 80% with a total sample size of 92. To be conservative we will use the larger sample size of 92 patients to ensure adequate power. With this sample size, the linear-mixed model will have 92% power to detect differences between groups with the same assumptions.

Statistical Analysis

General Principles

The statistical analyses and reporting will adhere to the CONSORT guidelines. All tests will be two-sided, a p-value <0.05 will be considered significant, and all confidence intervals will have 95% coverage. All analyses will be conducted on a modified intention-to-treat basis only including participants receiving at least the first dose of the study medication. In a double-blind trial, this approach is unbiased while increasing precision. Analyses will not be adjusted for covariates unless there are significant differences in baseline characteristics between study arms.

Baseline Characteristics

A description of the baseline characteristics will be presented by treatment arm. Categorical variables will be summarized by frequencies and percentages. Percentages will be calculated according to the number of patients for whom data are available. Continuous variables will be summarized using mean+/-standard deviation or median (interquartile range) based on the distribution of the data.

Analysis of Primary Outcome

We will compare repeated measures of lactate levels at each time point (0h, 6h, 12h, 24h) between arms using a linear mixed-effects model with an independent variance-covariance matrix to account for the correlation of within-patient repeated measures. Covariates in the model include treatment arm, time (as a categorical variable with four levels, defined as baseline, 6 hours, 12 hours, and 24 hours), and the interaction between treatment arm and time. Linear contrasts will be used to estimate the mean difference between treatment arms for each time point. If a patient dies before 24 hours, levels will be imputed by carrying forward the last known value before the event with a 20% penalty. A sensitivity analysis will be performed in which patients who die before 24 hours are assigned the last known value before the event without a penalty.

Analysis of Secondary Outcomes

Lactate levels over 72 hours

To test for a difference in absolute lactate level values, we will compare means or medians, as appropriate, between arms using either a Student's t-test or a Wilcoxon rank-sum test, respectively, at 6, 12, 24 and 72 hours.

Change in oxygen consumption (VO₂) over 48 hours

Prior to unblinding or analysis, oxygen consumption data will be cleaned using an algorithm designed by our research team in R version 4.1.1 (R Foundation for Statistical Computing, Vienna, Austria). This automated algorithm excludes VO₂ data (and the corresponding value for carbon dioxide production, or VCO₂) if one or more of the following criteria is met: all values recorded in the 10 min following a change in FiO₂ of 10%, all values recorded while FiO₂ is >61% (61% used in order to capture all situations when the ventilator is set for an FiO₂ of 60% or less, as the monitor reports this number to two decimal places and a set number of 60% may be recorded as 60.54%), all values deviating 15% or more from the mean of the previous five values and the next five values (i.e, deviating 15% from the mean of the ten neighboring data points), and all VO₂ values out of physiologic range unless these are persistent for more than 30 minutes, as these measurements are considered artifacts. Values that will be considered out of physiologic range are VO₂<80 mL/kg/min or VO₂>800 mL/kg/min. We allow these values if they persist for at least 30 min and if they are not excluded per the algorithm for other reasons, as critically ill post-arrest patients can sometimes have values well outside of standard normal range, due to temperature, medication use such as sedatives and neuromuscular blockade and/or alterations in metabolic function. The respiratory quotient (RQ) is calculated as the ratio of VCO₂/VO₂ at each time point. After data is run through the algorithm and still prior to unblinding, there is a final visual review of a graphical print-out of all data points for each patient to provide a secondary confirmation that values were kept or dropped appropriately.

To investigate the association between treatment and gas metabolism data (VO₂, VCO₂ and RQ) in the first 48 hours after ROSC, we will compare the area under the curve (AUC) for each oxygen consumption variable between the treatment arms. The AUCs for the oxygen consumption variables are influenced by the number of minutes of data available, which varies between patients. To account for this, AUCs for each patient will be adjusted by dividing by the number of minutes of oxygen consumption data available for that patient. Additionally, the AUCs for the VO₂ and VCO₂ variables are influenced by the weight of the patient, and thus will also be adjusted by dividing by the bodyweight of the patient, in kilograms. The median AUCs will be compared between treatment groups using the univariate Wilcoxon rank-sum test. To

control for the known effect of temperature on oxygen consumption, we will use quantile regression to compare median AUCs between patients using the treatment assignment as the predictor and average temperature as a covariate. To examine the association between treatment and the VO₂:Lactate Ratio, we will use a linear quantile mixed model (LQMM) with the VO₂:Lactate Ratio as the outcome variable, treatment as the predictor variable and temperature as the covariate. To account for clustering of VO₂:Lactate Ratio and temperature measurements within patients, we will add a random intercept for each patient to the LQMM. We will not control for vasopressor use or sedation in the above analyses unless use of these agents is significantly imbalanced between arms.

Pyruvate dehydrogenase (PDH), S100, NSE, SOFA score, creatinine, and cellular oxygen consumption rate levels over 72 hours

To test change over time, we will compare repeated measures of each outcome listed above at each time point (0h, 24h, 72h) between arms using a linear mixed-effects model with an independent variance–covariance matrix to account for the correlation of within-patient repeated measures. Covariates in the model include treatment arm, time, and the interaction between treatment arm and time. Linear contrasts will be used to estimate the mean difference between treatment arms for each time point. To test for a difference in absolute values between arms, we will compare means or medians, as appropriate, using either a Student’s t-test or a Wilcoxon rank-sum test, respectively, at 24 and 72 hours.

Mortality, Cerebral Performance Category (CPC) Score, and Cerebral Performance Category-Extended (CPC-E) Score at hospital discharge, 30 days, and 90 days

Proportions of patients who do not survive to hospital discharge, 30 days, and 90 days will be compared between treatment arms using Fisher’s exact test. Fisher’s exact test will also be used to compare the proportion of patients who have a favorable CPC score at the same time points, with favorable CPC score defined as a score of 1-2 and unfavorable a CPC of 3-5. CPC-E will be analyzed between treatment arms as a continuous variable in survivors to the time point of interest using either a Student’s t-test or a Wilcoxon rank-sum test, based on the distribution of the data.

Acute renal failure in the first 7 days after study drug initiation

Acute renal failure in the first 7 days after study drug initiation will be determined using the Kidney Disease Improving Global Outcomes (KDIGO) criteria for Stage 3 acute kidney injury/kidney failure. These criteria are as follows:

1. An increase in creatinine to $\geq 3 \times$ baseline (baseline defined as enrollment [post-arrest pre-study drug] creatinine value) OR
2. An increase in creatinine by $\geq 0.3\text{mg/dL}$ from baseline to $\geq 4\text{mg/dL}$ OR
3. Initiation of renal replacement therapy

Patients who die before 7 days and who do not meet the above criteria before death or transition to comfort measures only status will be classified as not having acute renal failure. Proportions of patients who have renal failure will be compared between groups using Fisher's exact test. Patients who already have end-stage renal disease (defined as being on dialysis/renal replacement therapy prior to arrest) will be excluded from the acute renal failure analysis.

Additional Planned Analyses

Pre-planned subanalyses of the primary outcome and of the secondary outcomes of mortality and VO_2 will be performed stratified by arrest duration, dichotomized into <15 minutes and ≥ 15 minutes and in the group of patients with baseline thiamine deficiency (plasma vitamin B1 level ≤ 7 nmol/L). Based on feedback from the DSMB, we will also perform subanalyses based on 0 hour lactate, stratified by ≤ 5 and >5 .

Analysis of Adverse Events

Rates of serious expected and unexpected adverse events will be reported by arm assignment. Proportions of patients with adverse events will be compared between the treatment arms using Fisher's exact test.

Statistical Software

Stata (version 17, StataCorp, College Station, Tx) & R (version 4.1.1, R Foundation for Statistical Computing, Vienna, Austria) will be used for all analyses and graphics.

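### No planned analysis estimates the change half of the VO₂ outcome, the VO₂ analyses ignore which hours were recorded, and monitoring and analysis use different 48-hour clocks

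*SAP*

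**What the plan says.** The first item under Secondary Outcomes is "Absolute level and change in VO₂ over 48 hours", so level and change are both promised. The matching part of Analysis of Secondary Outcomes is headed "Change in oxygen consumption (VO₂) over 48 hours".

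The method in that section is: "we will compare the area under the curve (AUC) for each oxygen consumption variable between the treatment arms". Because recording time differs between patients, each AUC is "adjusted by dividing by the number of minutes of oxygen consumption data available for that patient"; VO₂ and VCO₂ are also divided by body weight. Arms are compared by a Wilcoxon rank-sum test, then by quantile regression on arm and average temperature. A third analysis, a linear quantile mixed model (LQMM) of the VO₂:lactate ratio, has "treatment as the predictor variable and temperature as the covariate", plus a random intercept per patient.

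The analysis window is "in the first 48 hours after ROSC". The VO₂ monitoring paragraph of the Protocol section counts differently: patients are connected at enrolment or "as soon as the ventilator criteria are met, if still within 48 hours of enrollment". The cleaning algorithm then removes, among other values, those recorded at high FiO₂.

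**The concern.** An AUC divided by its own duration is a mean. Followed exactly, the plan would report an average level under a heading that says change, and the change half of the outcome would have no estimate.

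Dividing by minutes settles how much was recorded, but not when. A patient who met the ventilator criteria late contributes a mean over later hours, and that mean is compared directly with one taken over early hours. If VO₂ drifts after arrest, part of the spread between patients is timing. The ratio model has the same gap, and its denominator is known to move with time. The two clocks leave it unclear which minutes belong to the analysis.

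At stake are this secondary outcome and the VO₂ subanalyses under Additional Planned Analyses, which inherit the method.

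**Working it through.** The SAP gives no VO₂ mean, SD or trend, so there is no stated figure to reproduce. Steps 2 to 4 use assumed VO₂ values in mL/kg/min, for illustration only.

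**1. Terms in each planned analysis (SAP, Analysis of Secondary Outcomes)**

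| Analysis | Terms | Time, baseline or change? |
|---|---|---|
| Wilcoxon on AUC per minute | arm | none |
| Quantile regression of the same AUC | arm, average temperature | none |
| LQMM of VO₂:lactate | arm, temperature, patient intercept | none |
| PDH, S100, NSE, SOFA, creatinine, cellular oxygen consumption (mixed model) | arm, time, arm × time | time and arm × time; level tested separately |

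The last row shows that the SAP distinguishes change from level for other markers with the same two-part outcome. VO₂ gets only the level.

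**2. What AUC per minute can show.** For a straight path over 0-48 h, AUC/minutes is the average of the start and end values.
- Rising: (2.5 + 3.5)/2 = 3.00, change +1.0
- Falling: (3.5 + 2.5)/2 = 3.00, change −1.0
- Flat: 3.00, change 0

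Three different changes give one score.

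**3. Effect of which hours are recorded.** Let every patient follow 2.5 + D·t/48, with no treatment effect. The mean over a window from s to e is 2.5 + D·(s + e)/(2 × 48). So 0-24 h gives 2.5 + 0.25D, 24-48 h gives 2.5 + 0.75D, and the gap is 0.5D.

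| D (rise over 48 h) | 0-24 h | 24-48 h | Gap |
|---|---|---|---|
| 0 | 2.50 | 2.50 | 0 |
| 0.25 | 2.56 | 2.69 | 0.13 |
| 0.5 | 2.63 | 2.88 | 0.25 |
| 1.0 | 2.75 | 3.25 | 0.50 |

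Dividing by minutes does not remove the gap.

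**4. Does this reach the comparison between arms?** Simulation with no treatment effect: 46 per arm (92/2, as if all patients were monitored), between-patient SD 0.7, start times uniform over 12 h, recording to 48 h, 3,000 runs, two-sided 5% Wilcoxon test. One arm starts later by the stated shift, which moves its mean by D × (shift/2)/48.

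| D | No shift | 12 h shift | 24 h shift |
|---|---|---|---|
| 0 | 4.6% | 5.0% | 5.1% |
| 0.5 | 4.6% | 7.8% | 12.7% |
| 1.0 | 4.2% | 12.4% | 37.4% |

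Simulation error near 5% is √(0.05 × 0.95/3000), about 0.4 percentage points. Rejection rises only when there is both a trend and a shift between arms.

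**5. Ratio model.** Sample Size Calculations gives mean lactate of 3.8, 3.5 and 2.9 mmol/L at 6, 12 and 24 h. At constant VO₂, a ratio formed from these means rises by 3.8/2.9 − 1 = 31% from 6 h to 24 h with no treatment effect. This is a ratio of means, so it indicates scale only.

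**6. Clocks.** If enrolment is d hours after ROSC (d up to about 4.5), the analysis window closes 48 − d hours after enrolment, but connection is allowed until hour 48. A patient connected in the last d hours contributes no analysable minutes.

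**The case against.** The plan does recognise unequal monitoring. It divides by minutes and adjusts for average temperature, and the resulting mean is a legitimate summary of level. The trial is randomised and double-blind with one connection rule for both arms, so monitoring windows may well have the same distribution in each. All of this stands. It answers the level half of the outcome and limits the timing problem, but it supplies no estimate of change, and average temperature is not a substitute for time.

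Several stronger readings are tempting and are not supported:
- A reader might infer that timing differences turn into treatment differences. They do so only if windows differ by arm. Ventilator eligibility, extubation and death occur after randomisation and could cause that, but the SAP does not show that they do.
- A reader might take the gaps in step 3 as the error in the treatment effect. They compare individual patients at two extreme windows under an assumed trend.
- A reader might infer that the pre-dose lactate dilutes the ratio effect by a fixed fraction, such as one in four. The SAP does not say which VO₂-lactate pairs enter the model, and patients connected late have no time-0 pair.
- A reader might suppose that the AUC is inflated by bridging removed stretches. The SAP does not say that it bridges them; integrating over retained minutes only is at least as natural a reading.
- A reader might convert the clock mismatch into a percentage of data lost. The 48 h from enrolment limits when a patient may be connected and does not fix how long recording runs, so no loss can be computed.
- First place in the list does not imply priority. The SAP sets no hierarchy among secondary outcomes.

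**Conclusion.** The point holds in three parts that rest on the text alone: change in VO₂ has no estimator, the VO₂:lactate model has no time term despite a falling denominator, and the analysis and monitoring windows start from different origins. The first is a mismatch between outcome and method, since the SAP specifies a suitable model for its other repeated markers.

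The timing of monitored hours is a conditional concern. With like windows in both arms it adds noise, and rejection stays at about 4-5%. With an assumed SD of 0.7 and a trend of 0.5 to 1.0, false positives reach 8-12% for a 12 h shift between arms and 13-37% for a 24 h shift. No such shift is documented.

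The effect is confined to this secondary outcome, the ratio analysis and the VO₂ subanalyses. It is worth correcting before analysis; the primary lactate analysis is unaffected.

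**What to change.** - **Level:** keep the per-minute AUC, and state that it is computed over retained minutes only.
- **Change:** add a repeated-measures model of VO₂, VCO₂ and RQ in a few prespecified time bins, with arm, time, arm × time, temperature and a patient random effect. Report the arm difference in change by contrasts. Eight 6-hour bins would need 7 interaction terms; hourly categories would need 47, too many for at most 92 patients. Keep temperature, because the SAP already adjusts for its known effect.
- **Ratio:** add time and arm × time to the VO₂:lactate model, state which pairs enter, and take the treatment effect from post-dose times.
- **Clock:** use one time origin for monitoring and analysis throughout.

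If the sponsor does not want a model for change, the minimum is to define a per-patient change measure or remove change from the outcome and heading.

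The cost is SAP wording and modest programming on data that the plan already records continuously; the SAP says that it precedes any analysis. The model does need a within-patient correlation assumption that a single AUC avoids, and a missing-at-random assumption for late connection, extubation and death.

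### All secondary tests are judged at p<0.05 with no hierarchy, deciding comparison or exploratory label, and some differences are compared by two methods

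*SAP*

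**What the plan says.** Under Statistical Analysis, General Principles, the SAP states: "All tests will be two-sided, a p-value <0.05 will be considered significant". The rule does not separate primary from secondary outcomes. Outcome Measures lists one primary outcome (lactate change over 24 hours) and 12 secondary outcomes, but the label has no consequence for inference anywhere in the document.

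Two methods are planned for the same or nearly the same quantity in three places:

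- **PDH, S100, NSE, SOFA, creatinine and cellular oxygen consumption.** A mixed model is fitted at 0, 24 and 72 hours, and "Linear contrasts will be used to estimate the mean difference between treatment arms for each time point". The section then adds: "To test for a difference in absolute values between arms, we will compare means or medians, as appropriate", by t-test or Wilcoxon test at 24 and 72 hours.
- **VO₂, VCO₂ and RQ.** "The median AUCs will be compared between treatment groups using the univariate Wilcoxon rank-sum test". For the same AUCs, "we will use quantile regression to compare median AUCs between patients using the treatment assignment as the predictor and average temperature as a covariate".
- **Lactate.** The primary model gives between-arm contrasts at each time point to 24 hours. The secondary analysis compares levels by t-test or Wilcoxon test, "respectively, at 6, 12, 24 and 72 hours".

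**The concern.** Many trials leave secondary outcomes unadjusted but say that the results are exploratory. This plan instead gives a rule under which any secondary p-value below 0.05 is called significant. The secondary list includes mortality, neurologic outcome, NSE, S100 and renal failure, while the sample size rests on lactate alone. Followed literally, the plan would let one isolated p<0.05 among several dozen comparisons be reported as a significant effect of thiamine.

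The paired methods add a separate problem that needs no error-rate calculation. A mixed-model contrast and a Wilcoxon test, or an unadjusted and a temperature-adjusted comparison, can fall on opposite sides of 0.05. The plan does not say which one is the result.

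**Working it through.** The document states no familywise error rate, so there is no figure to reproduce. The check counts the planned tests and then sizes the error.

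**Count, from the sections on secondary outcomes**

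| Outcome | Tests |
|---|---|
| Lactate level at 6, 12, 24, 72 h | 4 |
| AUC of VO₂, VCO₂, RQ by Wilcoxon | 3 |
| Same AUCs by quantile regression | 3 |
| VO₂:lactate ratio, quantile mixed model | 1 |
| Eight 72-hour outcomes (PDH quantity, activity and specific activity; S100; NSE; SOFA; creatinine; cellular oxygen consumption): contrasts at 24 and 72 h, 8 × 2 | 16 |
| Same eight outcomes: t-test or Wilcoxon at 24 and 72 h, 8 × 2 | 16 |
| Mortality at 3 times | 3 |
| Favorable CPC at 3 times | 3 |
| CPC-E at 3 times | 3 |
| Acute renal failure | 1 |
| **Total** | **53** |

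The total leaves out 0 h contrasts, adverse events and all subgroup analyses. If the contrasts are estimates only and each of the eight mixed models gives one interaction test, the total is 53 − 16 + 8 = 45.

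**Duplication on the 53 reading.** 16 level differences plus 3 AUC differences make 19 tested twice, leaving 53 − 19 = 34 distinct differences. Separately, lactate at 6, 12 and 24 h repeats three contrasts of the primary model.

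**Expected number of p<0.05 if thiamine affects none of these outcomes.** 53 × 0.05 = 2.65 and 45 × 0.05 = 2.25. These expectations do not depend on correlation. Fisher's exact test usually has a true size below 0.05. If it is assumed to be 0.03 for the seven mortality, CPC and renal failure tests, the first figure becomes 46 × 0.05 + 7 × 0.03 = 2.51.

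**Chance of at least one, if independent: 1 − 0.95^k**

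- k = 53: 93.4%
- k = 45: 90.1%
- k = 34: 82.5%
- k = 12 (one test per listed outcome): 46.0%

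**Chance of at least one, with correlation.** The 53 test statistics were simulated under no effect, with 40,000 runs per setting. The assumptions were a correlation of 0.95-0.99 between two methods for the same difference, 0.5-0.9 between times within an outcome, 0.9 among the mortality and CPC tests, and a size of 0.03 for the Fisher tests. The document supplies none of these.

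| Correlation between different outcomes | Chance of at least one p<0.05 |
|---|---|
| 0 | 69-81% |
| 0.3 | 59-71% |
| 0.5 | 47-56% |
| 0.6 | 40-46% |

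The range over 0 to 0.6 is therefore about 40-81%. At 0.7 and 0.8 the simulation gives 34-37% and 26-28%, still several times 5%.

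**The case against.** The strongest defence is that the trial has one primary outcome, the sample size rests on it, and nothing claims confirmatory status for the rest. On that view, adjusting secondary outcomes in a 92-patient trial is a reporting preference. It is true that the plan does not claim confirmatory status. But it does not disclaim it either, and its significance rule covers all tests. A label would answer most of the point, and that is what the fix asks for.

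The duplication is also partly deliberate. Outcome Measures lists both absolute level and change for these outcomes, and the analysis section assigns the mixed model to change and the t-test or Wilcoxon test to level. However, the only contrasts specified are between-arm differences at each time point, which are level differences. If they are treated as estimates, the double testing is confined to the three gas-exchange AUCs. There, the pair is an unadjusted and an adjusted analysis, and the General Principles make unadjusted analysis the default. That arguably favours the Wilcoxon test, but the plan does not say so.

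A third objection concerns the count. Five of the tests (two each for VCO₂ and RQ, one for VO₂:lactate) concern variables not named in the list of secondary outcomes. Without them the totals are 48 and 40. This stands, but it does not change the conclusion.

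Finally, a reader might infer that the chance of a false positive is 93%, or that one is more likely than not whatever the data look like. The documents do not support either. The first figure treats 53 tests as independent when up to 19 pairs address the same difference. The second needs no true effect on any outcome and a between-outcome correlation below about 0.5. Nor does the plan declare every comparison significant; it sets the threshold by which each is judged.

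**Conclusion.** The point holds as a lack of protection for secondary claims, not as an established false-positive rate. The SAP judges about 45 to 53 secondary comparisons at p<0.05 with no hierarchy, deciding comparison or exploratory label. On the larger count it tests 19 differences twice.

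Under no effect on any outcome, 2 to 3 results below 0.05 are expected. The chance of at least one is roughly 40-81% for assumed between-outcome correlations of 0 to 0.6. The exact value cannot be known from the document and is not needed: under every setting examined it is far above 5%. The absence of a deciding comparison is a defect whatever the correlations are. The primary outcome is untouched by this point.

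**What to change.** In General Principles, reserve the word *significant* at 0.05 for the primary lactate outcome. State that secondary outcomes are reported as estimates with 95% confidence intervals and are hypothesis-generating.

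In the secondary-outcome sections, name in advance one deciding comparison per outcome and label the other supportive:

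- for levels, either the mixed-model contrast or the t-test/Wilcoxon test;
- for the AUCs, either the unadjusted or the temperature-adjusted comparison.

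Either choice is acceptable. Neither method has to be dropped, and the Wilcoxon option keeps some value for skewed data. A formal adjustment such as Holm over the named comparisons is needed only if the sponsor wants to make secondary claims of significance.

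The reservation works only if it is also clear which lactate comparison decides the primary outcome, since that model yields an interaction and several contrasts.

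The change requires SAP wording and no new data, but should be made before unblinding. Its price is that an isolated secondary p<0.05 can no longer be called significant, and the sponsor must commit to one method per outcome before seeing the distributions by arm.
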